2 STUDY OBJECTIVES

2.1 Primary Objectives

Safety

- Proportion of subjects without any localized or systemic safety events through 30 days that affect the access or venous outflow circuit and resulted in surgery, hospitalization, or death
 - Safety events in this calculation will not include venous outflow obstructions, which are captured in the calculation of Assisted Primary Patency of the target lesion, Assisted Primary Patency of the venous outflow circuit and Index of Patency Function

Effectiveness

- Proportion of subjects with Target Lesion Primary Patency at 30 days
 - Time to loss of Target Lesion Primary Patency is defined as the time interval of uninterrupted patency from initial study procedure to the next intervention performed on the target lesion or uncorrectable target lesion occlusion, whichever occurs first

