2.2 Secondary Objectives

- Proportion of subjects with Target Lesion Primary Patency at 3, 6 and 12 months
- Proportion of subjects with Assisted Primary Patency of the target lesion at 30 days, 3, 6 and 12 months
 - Time to loss of Assisted Primary Patency of the target lesion is defined as time following study procedure until uncorrectable target lesion occlusion
- Proportion of subjects with Primary Patency of the venous outflow circuit at 30 days, 3, 6, and 12months
 - Time to loss of Primary Patency of the venous outflow circuit is defined as the time following initial study procedure until the next venous outflow circuit intervention
- Proportion of subjects with Assisted Primary Patency of the venous outflow circuit at 30 days, 3, 6 and 12 months.

- Time to loss of Assisted Primary Patency of the venous outflow circuit is defined as the time following initial study procedure until complete access abandonment.
- Index of Patency Function at 3, 6 and 12 months, defined as time from initial study procedure to complete access abandonment divided by number of venous outflow circuit re-interventions to maintain hemodialysis
- Procedure or device related adverse events at 3, 6 and 12 months
- Clinical Success
 - The resumption of successful dialysis through existing access for at least one session following initial study procedure
- Anatomic Success
 - Less than 30% residual stenosis immediately following study procedure
- Procedural Success
 - The achievement of both clinical and anatomic success

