3.2 Exclusion Criteria

1. Subject has undergone a surgical intervention of the AVF/AVG ≤ 30 days from the date of the initial study procedure
2. Subject has had a previous stent or stent graft placed in the venous outflow circuit ≤ 30 days from the date of the initial study procedure
3. Active hemodialysis access is not in the arm
4. A pseudoaneurysm is present within the target lesion
5. Target lesion is:
 - a. in the superior vena cava
 - b. in the jugular vein
 - c. under the clavicle
 - d. requires stent graft placement across the elbow
 - e. in the needling segment of an AVF or AVG anastomosis
 - f. located within a stent
6. Lesions, other than the target lesion, in the venous outflow circuit with $>30\%$ stenosis
 - a. Note that subjects with secondary lesions may be included IF the lesions have been treated > 30 days before study procedure AND have less than 30% residual stenosis

7. Known or suspected infection of the hemodialysis access site and/or septicemia
8. Permanent pacemaker or automated implantable cardioverter defibrillator (AICD) on the side with the target lesion
9. Current central venous catheter for dialysis access
10. Uncorrectable coagulation disorders
11. Hypersensitivity to nickel titanium alloy
12. The subject is enrolled in another investigational study
13. The subject is unable or unwilling to comply with the protocol requirements
14. Life expectancy is ≤ 12 months
15. Subject cannot receive heparin or equivalent anticoagulant
16. Allergy to radiographic contrast material which cannot be adequately premedicated
17. Subject is pregnant, breastfeeding, or pre-menopausal and intending to become pregnant
18. Subject's access is anticipated to be abandoned within 3 months
19. Subject has a thoracic central vein obstruction that would lead to stent graft placement across the internal jugular vein
20. Subject's hemodialysis access is thrombosed
21. Active malignancy other than non-melanomatous skin cancer
22. Any other condition deemed exclusionary in the opinion of the investigator

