6 SUBJECT COMPLETION AND WITHDRAWAL

A subject is considered to have completed the study if he/she has had an initial study procedure and has follow-up information through 12 months.

Subjects will be informed that they have the right to withdraw from the study at any time for any reason, without prejudice to their medical care. The investigator also has the right to withdraw subjects from the

study for any reason. If a subject has a kidney transplant and/or current dialysis access is abandoned, he/she will be withdrawn from the study. If a subject is withdrawn from the study, the reason will be recorded on the end of study form. If a subject signs informed consent and is not enrolled in the study for any reason, the subject is a screen failure. A record of all subjects who signed an informed consent will be maintained.

Subjects will be considered lost to follow up if:

- The site has documented attempts to contact the subject at least three times without success, AND
- The site has a documented attempt to contact the subjects' dialysis center, AND
- The site has a documented attempt to contact the subjects' managing physicians

Subjects who are withdrawn from the study after completion of the study procedure for any reason will not be replaced. All subjects regardless of whether or not they complete the study, will be included in the Intent-to-Treat (ITT) population. The Sponsor may terminate the study at any time. In addition, termination or modification may be recommended for any other perceived safety concern based on clinical judgment of the Data Monitoring Committee (DMC) members.

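### Circuit Primary Patency has no loss event for a circuit that occludes or is abandoned without an earlier intervention, so it can exceed circuit Assisted Primary Patency

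*Combined protocol and SAP*

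**What the plan says.** Four definitions in the combined protocol and SAP bear on this.

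- **Circuit Primary Patency** (Section 2.2): the time to loss "is defined as the time following initial study procedure until the next venous outflow circuit intervention".
- **Circuit Assisted Primary Patency** (Section 2.2): the time to loss "is defined as the time following initial study procedure until complete access abandonment".
- **Target Lesion Primary Patency** (Section 2.1, repeated in Sections 4 and 9): it runs from the study procedure "to the next intervention performed on the target lesion or uncorrectable target lesion occlusion, whichever occurs first".
- **Index of Patency Function** (Section 2.2): "time from initial study procedure to complete access abandonment divided by number of venous outflow circuit re-interventions to maintain hemodialysis". The date of abandonment is therefore already needed.

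Section 9 lists circuit Primary Patency among the endpoints to be reported as a number and proportion, without redefining it. Section 6 withdraws a subject whose access is abandoned or who receives a transplant, has the reason recorded on the end of study form, and adds: "All subjects regardless of whether or not they complete the study, will be included in the Intent-to-Treat (ITT) population". No section states whether a subject withdrawn for abandonment counts as patent, lost, censored or missing for circuit Primary Patency.

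**The concern.** Primary patency is meant to be the stricter measure: it should be lost no later than assisted primary patency. Here the circuit version can be lost only through a further procedure. A circuit that fails and is given up without an attempt at repair meets no loss criterion, although it is a clear failure of the outcome being measured.

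The other definitions indicate that a limb is missing. The lesion endpoint allows for failure without treatment through its occlusion limb, and the circuit Assisted endpoint allows for it through abandonment. The circuit Primary endpoint does neither. If such subjects occur, the written rule errs in one direction, towards a higher patency rate, and the planned confidence interval does not reflect that error.

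**Working it through.** The plan gives no figure for this endpoint to reproduce, so the check is to apply the definitions to a subject and then to size the effect.

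**1. One subject under each definition.** Take a subject with no circuit intervention after the study procedure, whose target lesion occludes beyond correction and whose access is then abandoned.

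| Endpoint | Loss event as written |
|---|---|
| Target Lesion Primary Patency | at occlusion |
| Target lesion Assisted Primary Patency | at occlusion |
| Circuit Assisted Primary Patency | at abandonment |
| Circuit Primary Patency | none |

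This is out of order in two ways. Circuit Assisted is lost while circuit Primary is not. In addition, exclusion criterion 6 (Section 3.2) speaks of "Lesions, other than the target lesion, in the venous outflow circuit", which places the target lesion inside the circuit, yet an event that ends patency of the lesion does not end patency of the circuit containing it.

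**2. Does another section add the limb?** Section 8 has the committee adjudicate interventions. Section 12 has sites ask dialysis centers about revisions done elsewhere. Appendix A collects interventions since the last visit. All three concern procedures, and none adds occlusion or abandonment as a loss.

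**3. Extreme case of the reversal (assumed).** With n = 50, no circuit interventions and 3 subjects abandoned, Primary = 50/50 = 100% and Assisted Primary = 47/50 = 94%.

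**4. Size.** n = 50 is the approximate sample size in Section 9. Let L be the subjects with a circuit intervention and u the subjects whose circuit fails or is abandoned without one. Neither count is in the documents; L = 15 and the values of u below are assumptions.

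- Kept as patent: (n − L)/n
- Excluded: (n − L − u)/(n − u)
- Counted as a loss: (n − L − u)/n

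| u | Kept as patent | Excluded | Counted as a loss |
|---|---|---|---|
| 0 | 35/50 = 70.0% | 35/50 = 70.0% | 35/50 = 70.0% |
| 1 | 35/50 = 70.0% | 34/49 = 69.4% | 34/50 = 68.0% |
| 2 | 35/50 = 70.0% | 33/48 = 68.8% | 33/50 = 66.0% |
| 3 | 35/50 = 70.0% | 32/47 = 68.1% | 32/50 = 64.0% |

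If the subject is kept as patent, the overstatement is u/50, or 2.0 points per subject whatever L is. If the subject is excluded, it is smaller whenever L is at least 1: 69.4 − 68.0 = 1.4 points for u = 1 here.

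**5. Scale.** The plan promises confidence intervals without a level or method, so exact 95% intervals are assumed. The widest at n = 50 is for 25/50: 35.5% to 64.5%, a half-width of 14.5 points. Near the ceiling, one subject turns 49/50 (98.0%, 89.4% to 99.9%) into 50/50 (100%, 92.9% to 100%).

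**The case against.** The affected group is narrow and may be empty. Any attempted correction in the circuit already ends Primary Patency, so only a circuit given up with no attempt at all is missed. Two exclusion criteria make early cases less likely: "Subject's access is anticipated to be abandoned within 3 months" and "Subject's hemodialysis access is thrombosed". This stands, although the first covers only abandonment that is anticipated within 3 months, and the endpoint is also reported at 6 and 12 months.

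A reader might infer that the plan definitely counts these subjects as patent, because Section 6 keeps non-completers in an ITT population and Section 9 reports a simple proportion. The documents do not go that far. Section 9 defines only a Safety and an Efficacy population, assigns no outcome to ITT and states no denominator. The subject might be excluded or censored, or an analyst might score an abandoned circuit as not patent in the ordinary sense, in which case there is no overstatement. That makes the size conditional. It does not supply the missing loss event, since the written time-to-loss rule still has none.

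A reader might also want to count only abandonment caused by circuit failure. Added to circuit Primary Patency alone, that would not restore the order, because circuit Assisted Primary Patency ends at abandonment for any reason.

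**Conclusion.** The point holds as a defect in one definition. Circuit Primary Patency lacks an occlusion or abandonment limb, and followed as written it can exceed circuit Assisted Primary Patency. That follows from the text and needs no assumption.

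The size does rest on assumptions: 2.0 points per affected subject at n = 50 if the subject is kept as patent, less if excluded, and nothing if no such subject occurs. A few subjects would move the estimate by less than its random error.

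A reader might infer that the trial's main result is at risk. It is not. The 30-day primary effectiveness endpoint has its occlusion limb, abandonment still appears in circuit Assisted Primary Patency, and the study is single-arm with no comparisons planned. How withdrawals unrelated to patency should count is a separate question, common to all the patency endpoints, and forms no part of this point.

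**What to change.** In Section 2.2, and by reference in Section 9, define loss of circuit Primary Patency as the first of:

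1. the next venous outflow circuit intervention;
2. uncorrectable target lesion occlusion, which is already an event for the lesion endpoints;
3. complete access abandonment.

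Word the abandonment limb identically in the circuit Primary and circuit Assisted Primary definitions. If abandonment unrelated to circuit failure, for example after transplant, is to be treated as censoring, apply that to both definitions, using the withdrawal reason on the end of study form. Primary can then never be lost later than Assisted Primary. Because the target lesion lies within the circuit, circuit Primary Patency also cannot outlast lesion Primary Patency.

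The abandonment date is already needed for two other endpoints, and the occlusion event for the lesion endpoints. The cost is a possibly slightly lower reported rate and a small amount of work to classify abandonment reasons. The documents do not show whether the end of study form separates failure of the circuit from other reasons for abandonment, and Section 8 has the committee adjudicate interventions only, so someone must be assigned that classification.

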2.3 Exploratory Objectives

- Stent graft integrity (subset of subjects with thoracic central venous target lesions only)
 - Measured as freedom from stent graft fracture, defined as clear interruption of a stent strut observed in a minimum of two projections taken during the 12 Month visit or after determined by DMC/CEC examination of X-Ray images.

3 SUBJECT POPULATION

3.1 Inclusion Criteria

1. Subject has signed informed consent
2. Subject is ≥ 21 years of age
3. Subject is undergoing chronic hemodialysis or other forms of renal replacement therapy including transplantation, and has one of the following being used:
 - a. AV graft placed in the arm ≥ 30 days prior OR
 - b. Mature fistula in the arm with at least one successful dialysis session completed
4. Angiographic evidence of (multiple stenoses may exist within the target lesion):
 - a. a lesion less than 9 cm in length in an arm or thoracic central vein, not located within the needling segment of an AVF, and ends before the superior vena cava, OR
 - b. a lesion less than 9 cm in length in an arm or thoracic central vein, not located within the needling segment of an AVG venous anastomosis, and ends before the superior vena cava
5. The target lesion has $\geq 50\%$ stenosis
6. Subject has clinical or hemodynamic evidence of a venous outflow stenosis or obstruction
7. Full expansion of an appropriately sized standard angioplasty balloon (in the investigator's opinion) has been achieved during primary angioplasty at the target lesion prior to enrollment

3.2 Exclusion Criteria

1. Subject has undergone a surgical intervention of the AVF/AVG ≤ 30 days from the date of the initial study procedure
2. Subject has had a previous stent or stent graft placed in the venous outflow circuit ≤ 30 days from the date of the initial study procedure
3. Active hemodialysis access is not in the arm
4. A pseudoaneurysm is present within the target lesion
5. Target lesion is:
 - a. in the superior vena cava
 - b. in the jugular vein
 - c. under the clavicle
 - d. requires stent graft placement across the elbow
 - e. in the needling segment of an AVF or AVG anastomosis
 - f. located within a stent
6. Lesions, other than the target lesion, in the venous outflow circuit with $>30\%$ stenosis
 - a. Note that subjects with secondary lesions may be included IF the lesions have been treated > 30 days before study procedure AND have less than 30% residual stenosis

7. Known or suspected infection of the hemodialysis access site and/or septicemia
8. Permanent pacemaker or automated implantable cardioverter defibrillator (AICD) on the side with the target lesion
9. Current central venous catheter for dialysis access
10. Uncorrectable coagulation disorders
11. Hypersensitivity to nickel titanium alloy
12. The subject is enrolled in another investigational study
13. The subject is unable or unwilling to comply with the protocol requirements
14. Life expectancy is ≤ 12 months
15. Subject cannot receive heparin or equivalent anticoagulant
16. Allergy to radiographic contrast material which cannot be adequately premedicated
17. Subject is pregnant, breastfeeding, or pre-menopausal and intending to become pregnant
18. Subject's access is anticipated to be abandoned within 3 months
19. Subject has a thoracic central vein obstruction that would lead to stent graft placement across the internal jugular vein
20. Subject's hemodialysis access is thrombosed
21. Active malignancy other than non-melanomatous skin cancer
22. Any other condition deemed exclusionary in the opinion of the investigator

4 STUDY DESIGN

This is a phase 1 first in human study, designed to evaluate the safety and effectiveness of the WRAPSODY Stent Graft for the treatment of venous outflow circuit obstructions in the veins of the arm or thoracic central veins (brachiocephalic and/or subclavian) of subjects who receive chronic dialysis treatment for end stage renal disease.

The study will consist of a screening period in which subject eligibility will be determined. Approximately 50 subjects meeting the study entry criteria will be enrolled. Placement of the WRAPSODY stent graft will follow the procedure in Appendix B. Post study procedure subjects will have planned follow-up visits at 30 days (\pm 7 days), 3, 6 and 12months (\pm 4 weeks at each timepoint), and additional visits as referred by the subject's dialysis facility to assess access and venous outflow circuit patency, with revision if appropriate.

The primary study safety endpoint will be the proportion of subjects without any localized or systemic safety events through 30 days that affect the access or venous outflow circuit and resulted in surgery, hospitalization, or death. This calculation will not include venous outflow obstructions, which are

captured in the calculation of Assisted Primary Patency of the target lesion, Assisted Primary Patency of the venous outflow circuit and Index of Patency Function. Primary safety and effectiveness endpoints are at 30 days. Subjects will continue to be followed up to 12 months for supplementary information. The primary study effectiveness endpoint will be the proportion of subjects with Target Lesion Primary Patency at 30 days. Time to loss of Target Lesion Primary Patency is defined as the time interval of uninterrupted patency from initial study procedure to the next intervention performed on the target lesion or uncorrectable target lesion occlusion, whichever comes first.

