- Targeted physical exam, including at a minimum the following Clinical Indicators of Obstruction:
 - Assessment of edema in hand, arm, neck, head or trunk
 - Pain related to dialysis circuit
 - Respiratory symptoms
 - Neurological symptoms
 - Skin changes
- Adverse event review
- Interventions on venous outflow circuit since last visit
- Concomitant medications

Visit 4: 6 months (± 4 weeks)

- Targeted physical exam, including at a minimum the following Clinical Indicators of Obstruction:
 - Assessment of edema in hand, arm, neck, head or trunk
 - Pain related to dialysis circuit
 - Respiratory symptoms
 - Neurological symptoms
 - Skin changes
- Adverse event review
- Interventions on venous outflow circuit since last visit
- Concomitant medications

Visit 5: 12 months (± 8 weeks)

Traditional visit windows are being expanded for the 12-month visit to allow for potential impacts due to COVID-19.

- Targeted physical exam, including at a minimum the following Clinical Indicators of Obstruction:
 - Assessment of edema in hand, arm, neck, head or trunk
 - Pain related to dialysis circuit
 - Respiratory symptoms
 - Neurological symptoms
 - Skin changes
- Adverse event review
- Interventions on venous outflow circuit since last visit

- Concomitant medications
- X-rays of the treated area (subset of subjects with thoracic central venous target lesions only)
 - Minimum of two projections required to visualize WRAPSODY stent graft

Additional visits, as needed/referred for evaluation/treatment of venous outflow dysfunction

- Angiographic Evaluation, if medically indicated
- Clinical reason(s) subject was referred for obstruction evaluation
- Targeted physical exam, including at a minimum the following Clinical Indicators of Obstruction:
 - Assessment of edema in hand, arm, neck, head or trunk
 - Pain related to dialysis circuit
 - Respiratory symptoms
 - Neurological symptoms
 - Skin changes
- Interventions on venous outflow circuit since last visit
- Adverse event review
- Current intervention, if done, including:
 - Procedure type
 - Lesion location and length
 - % stenosis before treatment
 - % residual stenosis after treatment
- Concomitant medications
- X-rays of the treated area (subset of subjects with thoracic central venous target lesions only)
 - Subjects who were unable to have X-Rays completed at scheduled Visit 5 (12 Months) may be brought back for an additional visit to complete X-Rays after obtaining proper consent.

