9 STATISTICAL ANALYSIS

Analysis Sets

Safety Population: The safety population will include all enrolled subjects who received the treatment.

Efficacy Population: The efficacy population will include all enrolled subjects who received the treatment as specified in the protocol and met all eligibility criteria.

The primary safety endpoint is the proportion of subjects without any localized or systemic safety event through 30 days that affect the venous access circuit and resulted in surgery, hospitalization, or death. Safety events in this calculation will not include venous outflow obstructions which are captured in the calculation of assisted primary patency of the target lesion, assisted primary patency of the venous outflow circuit, and index of patency function. This is an observational study, and outcomes will be summarized, but no comparisons will be performed. Confidence intervals will be provided for all outcome calculations wherever possible.

The primary effectiveness endpoint is the proportion of subjects with target lesion Primary Patency at 30 days. Time to loss of target lesion Primary Patency is defined as the time interval of uninterrupted patency from initial study procedure to the next intervention performed on the target lesion or uncorrectable target lesion occlusion, whichever occurs first.

Sample Size

A sample size of approximately 50 subjects was chosen as appropriate for an initial safety and efficacy evaluation.

The primary effectiveness analyses of target lesion Primary Patency at 30 days will be summarized using number and proportion of subjects with Target Lesion Primary Patency at that timepoint.

This methodology will be repeated to test secondary endpoints, proportion of subjects with: target lesion Primary Patency at 3, 6, and 12 months; Assisted Primary Patency of target lesion at 3, 6, and 12 months; Primary Patency of the venous outflow circuit at 3, 6, and 12 months; Assisted Primary Patency of the venous outflow circuit at 3, 6, and 12 months.

The primary safety endpoint will be summarized using number and proportion of subjects without any localized or systemic safety event that affected the access or venous outflow circuit and resulted in surgery or hospitalization or death through 30 days.

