A formal interim analysis will be completed when all subjects complete the 6-month visit, (Visit 4), (or discontinue prior to the 6-month visit). As the interim analysis will be the primary effectiveness analysis, no alpha adjustment for multiplicity will be applied for this interim analysis. The final analysis will be completed when all subjects complete the study (12-month visit; Visit 5).

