APPENDIX A

Schedule of Study Events

Visit Schedule	Visit 1	Visit 2 ³ 30 days (\pm 7 days)	Visit 3 ³ 3 Months (\pm 4 weeks)	Visit 4 ³ 6 Months (\pm 4 weeks)	Visit 5 ³ 12 Months (\pm 8 weeks)	Additional Visits ³
Informed Consent	X					
Eligibility Criteria Assessment	X					
Demographics	X					
Vital Signs	X					
Medical History Relevant to Dialysis	X					
Current dialysis access	X					
Reason(s) for obstruction evaluation	X					X
Concurrent Medical Conditions	X					
Targeted Physical Examination (Clinical Indicators of Obstruction)	X	X	X	X	X	X
Serum Pregnancy Test (if applicable)	X					
Concomitant Medications	X	X	X	X	X	X
Angiographic Imaging	X					X ²
X-rays of treatment area ⁴					X	X ⁵
Enrollment	X					
Stent Graft Placement	X					
Hemodialysis Assessment		X				
Adverse Event ¹	X	X	X	X	X	X
Interventions on access and venous outflow circuit since last visit		X	X	X	X	X
Protocol Deviation	X	X	X	X	X	X

¹ Adverse Events to be collected beginning at time of study procedure

² If medically indicated

³ Every effort should be made to collect information by subject visit, however information may be obtained from the subject's dialysis clinic or managing physician if a visit is not possible

⁴ X-rays of treatment area for a subset of subjects with thoracic central venous target lesions only. All potential subjects will be reconsented prior to X-Ray imaging.

⁵ Only for those subjects with thoracic central venous target lesions who were unable to complete the x-rays at the 12-month follow up visit. X-rays are only requested at the 12-month time point or later.

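### The 12-month visit window is given two ways, and under either one the last scheduled visit can fall before 12 months with no rule for setting 12-month patency

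*Combined protocol and SAP*

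**What the plan says.** **The window.** Section 4 gives the 3-, 6- and 12-month visits a common tolerance of plus or minus "4 weeks at each timepoint". The Section 5 visit list has "Visit 5: 12 months (± 8 weeks", and the Appendix A schedule also shows 8 weeks. Section 5 gives the reason: "Traditional visit windows are being expanded for the 12-month visit to allow for potential impacts due to COVID-19".

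**Completion.** Section 6 counts a treated subject as complete if he or she "has follow-up information through 12 months". Section 9 ties completion to the visit itself: "The final analysis will be completed when all subjects complete the study (12-month visit; Visit 5").

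**Endpoint and analysis.** Section 2.2 lists "Proportion of subjects with Target Lesion Primary Patency at 3, 6 and 12 months", and the other patency measures are also due at 12 months. Section 2.1 defines loss of target lesion primary patency as a time, running from the study procedure to the next target lesion intervention or uncorrectable occlusion. Section 9 summarizes the 30-day result as the "number and proportion of subjects with Target Lesion Primary Patency at that timepoint" and repeats that method for the later timepoints.

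**Data capture.** At each follow-up visit the site asks about interventions back to the previous visit. Section 12 lets sites obtain status from the dialysis center or a treating physician when a subject cannot or will not attend. It also requires them to confirm with dialysis centers whether revisions were done elsewhere. No date is attached to that confirmation.

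**The concern.** There are two separate problems.

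The first is a plain contradiction in current text. A Visit 5 held six weeks from the nominal date is outside the window in Section 4 and inside it in Section 5 and Appendix A. Section 12 requires deviations to be captured, so sites need to know which applies.

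The second does not depend on which window is kept. Either one lets the last scheduled visit precede 12 months. An early Visit 2, 3 or 4 does little harm, because the next visit asks about the interval in between. Nothing scheduled follows Visit 5. If a subject attends early, has no intervention up to that day and is closed out, the simple proportion in Section 9 can count that subject as patent at 12 months although the last weeks were never observed. The error runs in one direction: unobserved losses can only raise the reported 12-month patency.

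**Working it through.** The plan gives no figure of its own here to reproduce.

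**Inputs**
- Half-width of the window: 28 days (Section 4) or 56 days (Section 5, Appendix A).
- 12 months = 365 days. This is an assumption; the documents give no day count.
- Sample size: about 50 (Sections 4 and 9).
- For illustration, primary patency of 81% at 6 months and 67% at 12 months, from the 42-subject central-vein stent-graft cohort described in Section 1.3.

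**Step 1: earliest compliant Visit 5**
- 4 weeks: 365 − 28 = day 337, leaving 28/365 = 7.7% of the year unobserved.
- 8 weeks: 365 − 56 = day 309, leaving 56/365 = 15.3% unobserved.
- Taking 12 months as 360 or 364 days moves these edges to days 332 or 336, and 304 or 308. The conclusion is the same.

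Reconciling the window therefore does not by itself remove the early edge.

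**Step 2: is the gap filled later?** Additional visits in Section 5 occur on referral, or to obtain missed X-rays in the thoracic central vein subset. No contact after Visit 5 is scheduled for every subject. A subject seen on day 309 with no further information satisfies the Section 9 wording on completion but not the Section 6 definition.

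**Step 3: upper bound on the shift.** Assume a constant hazard between 6 and 12 months, every Visit 5 at the early edge, and every subject patent at that visit counted as patent at 12 months.
- Hazard: h = ln(81/67)/6 = 0.0316 per month.
- With 365/12 = 30.42 days per month, 56 days = 1.84 months and 28 days = 0.92 months.
- 8 weeks early: 67 × exp(0.0316 × 1.84) = 71.0%, a shift of +4.0 points, or 2.0 of 50 subjects.
- 4 weeks early: 67 × exp(0.0316 × 0.92) = 69.0%, a shift of +2.0 points, or 1.0 of 50 subjects.

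**Step 4: sensitivity to the patency assumed.** With a constant hazard from the procedure onward, patency at day d is p^(d/365), where p is true 12-month patency.

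| True 12-month patency | Overstatement, day 309 | Overstatement, day 337 |
|---|---|---|
| 40% | 6.0 points (3.0 of 50) | 2.9 points (1.5 of 50) |
| 80% | 2.8 points (1.4 of 50) | 1.4 points (0.7 of 50) |

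**Step 5: a less extreme case.** If 20% of visits fell at the 8-week early edge (an assumption) and the rest reached day 365, the shift would be 0.2 × 4.0 = 0.8 points, or 0.4 of 50 subjects. For scale, the 95% half-width around 67% with 50 subjects is 1.96 × √(0.67 × 0.33/50) = 13.0 points.

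**The case against.** The case on the other side is substantial.

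- **The mismatch is explained.** Section 5 says the 12-month window was widened for COVID-19, and Appendix A agrees, so Section 4 was apparently not updated. That stands: this half is an editorial repair.
- **Section 6 already asks for information through 12 months, and the Section 12 confirmation with dialysis centers is mandatory.** Both are true and narrow the gap. An intervention at the study site after an early Visit 5 might also surface as an additional visit. But the confirmation has no date and could be made on day 309, and Section 9 lets completion follow the visit.
- **COVID-19 would more plausibly delay visits than bring them forward.** That is reasonable, and it makes the upper bound unlikely. The window is still symmetric and allows early visits.
- **The illustration rests on one small central-vein cohort**, while this trial also treats arm veins. Hence the range in Step 4.

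A reader might infer that late visits distort the result as well, since reading status at the 8-week late edge would give 63.2% instead of 67%. The documents do not support this. Loss of patency is a time from procedure to event, so an intervention on day 400 is not a loss at 12 months, and a late visit fully observes day 365.

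A reader might also infer that adverse event collection stops at an early Visit 5. Sections 7.1, 7.2 and 7.3 set a 12-month collection period that does not end with that visit.

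**Conclusion.** The contradiction between Section 4 on one side and Section 5 and Appendix A on the other is literal and must be reconciled. Separately, under either window a compliant last visit can leave 12-month patency unobserved for up to 28 or 56 days. Section 9 has no rule for such a subject.

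The possible error is an overstatement of 12-month patency. Its extreme bound is +4.0 points at 8 weeks or +2.0 points at 4 weeks with the cited 67%. Over true patency of 40% to 80%, the bound runs from 6.0 down to 2.8 points at 8 weeks. These figures need every visit at the early edge, a constant hazard and 12 months taken as 365 days. The realistic shift is smaller and well inside the sampling error of a 50-subject, single-arm summary.

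Only the secondary 12-month patency endpoints are affected. The primary endpoints are at 30 days, and Section 4 describes the later follow-up as supplementary. This is a minor point, worth fixing because the remedy is cheap and the bias has a known direction.

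**What to change.** 1. State one window for the 12-month visit in Section 4, Section 5 and Appendix A. The steps below work whichever window the sponsor keeps.
2. Add to Section 9 that 12-month patency is determined at day 365 from the dates of interventions and occlusions, so that events after day 365 do not count for that timepoint.
3. For any Visit 5 held before day 365, require the dialysis-center confirmation in Section 12 to be made on or after day 365, covering access status and interventions up to that day. This also brings the Section 9 wording on completion into line with Section 6.
4. If day-365 status cannot be obtained, treat the subject as censored at last contact. A simple proportion cannot carry censoring, so Section 9 should then give a Kaplan-Meier estimate at day 365 with its confidence interval.

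The cost is a text edit to align the window, a short addition to Sections 9 and 12, and a small records check for subjects seen early. No added subject visit is needed.
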